5.2.2. Pooling of centers

In order to provide overall estimates of treatment effects, data will be pooled across centers. The ‘center’ factor will not be considered in statistical models or for subgroup analyses due to the high number of participating centers in contrast to the anticipated small number of patients randomized at each center.

5.2.3. Presentation of continuous and qualitative variables

Continuous variables will be summarized using descriptive statistics ie, number of non-missing values and number of missing values [ie, n (missing)], mean, median, standard deviation (SD), minimum, maximum and first and third quartile (Q1 and Q3).

Qualitative variables will be summarized by frequency counts and percentages. Unless otherwise specified, the calculation of proportions will include the missing category. Therefore, counts of missing observations will be included in the denominator and presented as a separate category.

In case the analysis refers only to certain visits, percentages will be based on the number of patients still present in the study at that visit, unless otherwise specified.

5.2.4. Definition of study day

Start day of study treatment is the day of the first dose of study treatment in Arm A, and the day of Cycle 1 Day 1 in Arm B.

The study day for assessments occurring on or after the start of study treatment (eg, adverse event onset, tumor measurement) will be calculated as:

Study day = Date of the assessment/event - start of study treatment + 1.

The study day for assessments occurring prior to the first dose of study treatment (eg, baseline characteristics, medical history) will be negative and calculated as:

Study day = Date of the assessment/event - start of study treatment.

The study day will be displayed in all relevant data listings.

5.2.5. Definition of start of new anti-cancer drug therapy

Start date of new anti-cancer drug therapy is used to determine the end of the on-treatment period (see [Section 5.2.7](#)).

The start date of new anti-cancer drug therapy is the earliest start date of anti-cancer drug therapy recorded in the 'Follow-up Cancer Therapy' eCRF pages that is after the first dose of study treatment. When the start date of anti-cancer drug therapy is missing or partially missing, the imputation rules described in [Section 5.3.3.4](#) should be applied using only data from the 'Follow-up Cancer Therapy' eCRF pages.

5.2.6. Definition of start of new anti-cancer therapy

Start date of new anti-cancer therapy (drug, radiation, surgery) is used for censoring in efficacy analyses (see [Section 6.1.1](#) and [Section 6.2.2](#)).

The start date of new anti-cancer therapy is the earliest date after randomization amongst the following:

- Start date of anti-cancer drug therapy recorded in the 'Follow-up Cancer Therapy' eCRF pages
- Start date of radiation therapy recorded in 'Concomitant Radiation Therapy', and 'Follow-up Radiation Therapy' eCRF pages with 'Treatment Intent' = 'Curative in intent'
- Surgery date recorded in 'Concomitant Surgery', and 'Follow-up Surgery' eCRF pages when 'Surgery Outcome' = 'Resected' or 'Partially Resected'.

When start date of anti-cancer therapy is missing or partially missing, the imputation rules described in Section 5.3.3.4 should be applied using 'Follow-up Cancer Therapy', 'Concomitant Radiation Therapy', 'Follow-up Radiation Therapy', 'Concomitant Surgery', and 'Follow-up Surgery' eCRF pages.

5.2.7. Definition of on-treatment period

Safety endpoints will be summarized based on the on-treatment period unless otherwise specified. On-treatment period is defined as follows:

- Arm A: time from the first dose of study treatment through minimum (30 days + last dose of study treatment, start day of new anti-cancer drug therapy – 1 day);
- Arm B: time from Cycle 1 Day 1 through minimum (30 days + end date of BSC, start day of new anti-cancer drug therapy – 1 day).

Here, 'end date of BSC' is the date of completion or discontinuation as collected in the 'Disposition - Treatment Phase' eCRF page.

Safety data collected outside the on-treatment period as described above will be listed and flagged in listings but will not be summarized.

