5.4.3. Recommended Dose Modifications

Every effort should be made to administer study treatment on the planned dose and schedule.

For avelumab, no dose modifications are permitted in this study, but next infusion may be omitted based on persisting toxicity. Recommended toxicity management guidelines with regard to avelumab infusion omissions are shown in Table 3.

Table 3. Avelumab Infusion Omissions for Avelumab Product-Related Toxicity

| Toxicity | NCI CTCAE Severity Grade | Avelumab |
|---|--------------------------|---|
| | | Treatment Modification |
| Infusion-related Reaction / Hypersensitivity | Grade 1-4 | 
 See Section 5.4.3.2 and Table 4. |
| Tumor lysis syndrome | Grade 1-4 | 
 See Section 5.4.3.3 and Figure 2. |
| Immune-related AE (irAE) | Grade 1-4 | 
 See Section 5.4.3.4 and Table 5. |
| Drug-related adverse reactions (excluding infusion-related reaction / hypersensitivity and immune-related AE) | Grade 1 | 
 Continue as per schedule. |
| | Grade 2 | 
 Continue as per schedule. |
| | Grade 3 | 
 Withhold until recovery to Grade \leq1 or baseline. Permanently discontinue if toxicities do not resolve to Grade \leq1 or baseline within 12 weeks of last administration or if the same Grade 3 toxicity recurs. 
Exceptions are:
 
 Laboratory values out of normal range that do not have any clinical correlate. |
| | Grade 4 | 
 Permanently discontinue. 
Exceptions are:
 
 Laboratory values out of normal range that do not have any clinical correlate. |

Avelumab infusion-related reactions (including hypersensitivity) and irAEs should be handled according to guidelines in [Section 5.4.3.2](#) Management of Avelumab Infusion-Related Reactions and [Section 5.4.3.4](#) Management of Avelumab Immune-Related Adverse Events.

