3.4. Baseline Variables

3.4.1. Study drug, study treatment and baseline definitions

In this study, ‘study drug’ refers to avelumab or BSC and ‘study treatment’ (or ‘treatment arm’) refers to one of the following:

- Arm A = Avelumab + BSC;
- Arm B = BSC alone.

Start and end dates of study treatment:

- For Arm A:
 - The date/time of first dose of study treatment is the earliest date/time of non-zero dosing of the study drug.
 - The date/time of last dose of study treatment is the latest date/time of non-zero dosing of the study drug.

- For Arm B:
 - The date of start of study treatment is defined as the date of Cycle 1 Day 1 (C1D1); a patient is considered to be treated in Arm B if they complete the C1D1 visit.
 - ‘End date of BSC’ (last dose of study treatment) is the date of completion or discontinuation as collected in the ‘Disposition - Treatment Phase’ eCRF page.

Definition of baseline:

Definition of baseline for efficacy and PRO analyses

The last measurement prior to randomization will serve as the baseline measurement for efficacy and PRO analyses. If such a value is missing (since per protocol the first PRO assessment is planned to occur on Cycle 1 Day 1), the last measurement prior to the first dose of study treatment will be used as the baseline measurement except for analyses of tumor assessments data where the baseline assessment would be considered as missing.

Definition of baseline for immunogenicity analyses (Arm A only)

The last available assessment prior to the start of treatment with avelumab is defined as ‘baseline’ result or ‘baseline’ assessment. If an assessment is planned to be performed prior to the first dose of avelumab in the protocol and the assessment is performed on the same day as the first dose of avelumab, it will be assumed that it was performed prior to avelumab administration, if assessment time point is not collected or is missing.

Definition of baseline for safety analyses

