6.5.3. Study Treatment Compliance and Exposure

The following analyses will be based on the safety analysis set by treatment arm.

All dosing calculations and summaries will be based on 'Parenteral – Drug avelumab' eCRFs pages. A listing of study drug administration will be created with the information collected on the 'Parenteral – Drug avelumab' eCRF pages.

For Arm B, the duration of BSC treatment will be summarized based on the time from C1D1 through date of discontinuation of BSC as collected in the Disposition eCRF page.

The derivations below are provided for the following:

- Avelumab administered as a 1-hour IV infusion at a dose of 10 mg/kg once every 2 weeks in 4-week cycles.

Analysis of exposure will be based on the calculated actual dose levels:

- Avelumab - total dose / weight

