6.6.2. Deaths

The frequency (number and percentage) of patients in the safety analysis set who died and who died within 30 days after last dose of study treatment as well as the reason for death will be tabulated based on information from the ‘Notice of Death’ and ‘Survival Follow-Up’ eCRFs, by treatment arm.

- All deaths
- Deaths within 30 days after last dose of study treatment
- Reason for Death
 - Disease progression
 - Study treatment toxicity
 - AE not related to study treatment
 - Unknown
 - Other.

In addition, date and cause of death will be provided in individual patient data listing together with selected dosing information (study treatment received, date of first / last administration, dose) and will include the following information:

- AEs with fatal outcome (list preferred terms of AEs with outcome = Fatal, as well as AEs of Grade 5),
- Flag for death within 30 days of last dose of study treatment.

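### The 30-day safety window starts from a different kind of date in each arm, so the 30-day death count favours avelumab whenever the last infusion precedes discontinuation

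*SAP*

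**What the plan says.** SAP 3.4.1 defines the end of treatment separately by arm. For Arm A: "The date/time of last dose of study treatment is the latest date/time of non-zero dosing of the study drug". For Arm B, the end date of BSC carries the gloss "last dose of study treatment) is the date of completion or discontinuation as collected in the" Disposition - Treatment Phase page. One label therefore covers two kinds of event: a drug administration in Arm A and an administrative stop in Arm B.

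SAP 3.5.1 and 5.2.7 add 30 days to each date. Arm A runs "through minimum (30 days + last dose of study treatment, start day of new anti-cancer drug therapy" minus a day. Arm B runs "through minimum (30 days + end date of BSC, start day of new anti-cancer drug therapy" minus a day. Safety data outside this period are listed and flagged but not summarised.

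SAP 6.6.2 plans a row for "Deaths within 30 days after last dose of study treatment". It inherits the two dates and has no new-therapy cut. All deaths are tabulated as well. Immune-related events are handled separately: SAP Appendix 1 takes onsets up to 90 days after last dose, regardless of new therapy or treatment-emergent status.

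The SAP plans no common-date sensitivity analysis and no exposure-adjusted adverse-event rates.

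**The concern.** The last infusion normally comes before the decision to stop. In Arm B the date used is the stop itself. The 30 days in Arm A therefore begin earlier relative to stopping, and fewer of them fall after it. That matters most for deaths, because patients who stop for progression or deterioration may be at high short-term risk.

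The SAP's own exposure formulas show the mismatch. SAP 6.5.3.1 adds 14 days to the interval between first and last avelumab dose, so each infusion is credited with its two-week interval. SAP 6.5.3.6 measures BSC to its end date plus one day. The safety window drops the two-week credit, and only Arm A is affected.

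At stake is a between-arm mortality row in an open-label trial against supportive care. It could show fewer early deaths on avelumab when the true rates are the same.

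**Working it through.** The plan states no figure to reproduce here, because this is a window definition. The check is arithmetic on the window.

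**Inputs from the documents**
- Dosing interval: 14 days (SAP 6.5.3: "Avelumab administered as a 1-hour IV infusion at a dose of 10 mg/kg once every 2 weeks in 4-week cycles"). Without a hold, g, the number of days from last infusion to discontinuation, is about 0 to 14.
- Longest hold described: Protocol Table 3 requires permanent discontinuation if toxicity has not resolved "within 12 weeks of last administration or if the same Grade 3 toxicity recurs". For a patient who never resumes, g can approach 84 days.
- Survival after stopping: not given. **Assumption:** the second-line medians of 4.6 to 6.9 months in Protocol 1.2.3.1 as a proxy, exponential, equal in both arms.

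**30-day deaths**

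Window after stopping: Arm A max(0, 30 − g) days; Arm B 30 days. Risk over d days = 1 − exp(−ln 2 × d / (median × 30.4375)).

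| g (days) | Arm A window | Arm A vs B, median 6.9 mo | Arm A vs B, median 4.6 mo |
|---|---|---|---|
| 0 | 30 | 9.4% vs 9.4% | 13.8% vs 13.8% |
| 7 | 23 | 7.3% vs 9.4% (2.1 points) | 10.8% vs 13.8% (3.0 points) |
| 14 | 16 | 5.1% vs 9.4% (4.3 points) | 7.6% vs 13.8% (6.2 points) |
| 28 | 2 | 0.7% vs 9.4% (8.8 points) | 1.0% vs 13.8% (12.8 points) |

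These are percentages of patients who stop alive. Differences are taken before rounding.

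The full row also contains deaths during treatment, which dilute the loss. **Further assumptions:** median time to discontinuation 5.3 months (the placebo PFS of the cited lapatinib maintenance study), a pre-progression death median of 60 months, and g uniform on 0 to 14 days. The share dying before discontinuation is (1/60) / (1/60 + 1/5.3) = 8.1%, counted in both arms. Averaging the Arm A risk over g gives 7.3% (6.9 months) and 10.7% (4.6 months).
- Median 6.9: Arm A 8.1% + 91.9% × 7.3% = 14.8%; Arm B 8.1% + 91.9% × 9.4% = 16.8%. The Arm A row loses about 12%.
- Median 4.6: Arm A 8.1% + 91.9% × 10.7% = 18.0%; Arm B 8.1% + 91.9% × 13.8% = 20.8%. The row loses about 13.5%.

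**Treatment-emergent events**

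Let s be days from stopping to new drug therapy. Days counted after stopping: Arm A max(0, min(30 − g, s − 1)); Arm B min(30, s − 1). At g = 14:
- no new drug within 30 days: 16 vs 30
- s = 28: 16 vs 27
- s = 21: 16 vs 20
- s = 17 or earlier: equal
- Arm B starting on day 14 and Arm A late: 16 vs 13, so the order reverses.

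Crude incidence also depends on time on treatment. At an assumed equal rate of 0.1 per 30 days and g = 14:
- 60 days on treatment in both arms: Arm A 1 − exp(−0.1 × 76/30) = 22.4%; Arm B 1 − exp(−0.1 × 90/30) = 25.9%.
- 90 days in Arm A and 60 in Arm B: Arm A 1 − exp(−0.1 × 106/30) = 29.8%; Arm B 25.9%.

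The net sign is not fixed.

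**The case against.** The strongest reply is that the windows follow the trial's own schedule. Arm A follow-up visits fall 30, 60 and 90 days after last dose and Arm B visits the same intervals after the end-of-treatment visit, and adverse-event collection uses the same pair of dates (Protocol 8.2). Moving the whole on-treatment definition would break that alignment: Arm A 30-day visits would fall inside the new window, while Arm B visits on days 31 to 33 could fall outside. This stands, and it argues against replacing SAP 5.2.7 as the primary definition.

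The gap may also be small. Protocol 7.8 asks sites to keep patients on treatment until central review of progression is complete, which can shorten g. That carries less weight for patients who stop for toxicity or clinical deterioration, since Protocol 7.7 limits the expectation to patients without deterioration. All deaths are tabulated too, and OS from randomisation is compared without any such window.

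A reader might infer three stronger things that the documents do not support.
- That all safety tables tilt toward avelumab. The new-therapy cut can remove or reverse the difference, longer treatment in Arm A pushes crude percentages the other way, and the 90-day immune-related window is not governed by this rule. Fatal adverse events enter by onset date, so the death-date arithmetic does not carry over to them.
- That any Arm A patient held for more than 30 days leaves the on-treatment period. The window runs to the latest non-zero dose, so a patient who resumes never leaves it. Only those who never resume do, and then only onsets more than 30 days after the final infusion are lost.
- That serious events cluster around stopping. Protocol 8.6 says hospitalisation for signs and symptoms of progression should not be reported as serious, and no passage documents such clustering.

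**Conclusion.** The point holds for the 30-day death row. The two starting dates differ in kind, no new-therapy cut intervenes, and at equal mortality the row can only favour avelumab when g exceeds zero. This assumes that the last infusion is never later than the recorded discontinuation.

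The size rests on g, which the documents do not give, and on the assumed survival after stopping. Plausible values without a hold run from no difference to 4.3 to 6.2 points among patients who stop. With g spread evenly over 0 to 14 days, the whole row loses about 12% to 13.5% under the further assumptions above. Giving every patient a 14-day gap would remove about 45% of deaths after stopping (5.1% against 9.4%), but that is the top of the no-hold range and should not be read as the expected effect.

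For treatment-emergent events, serious events and laboratory data, the period after stopping is also shorter in Arm A unless new drug therapy starts early. The net direction of those full tables is not established. This is a worthwhile, inexpensive correction; it does not undermine the safety analysis as a whole.

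**What to change.** In SAP 6.6.2, count the between-arm 30-day deaths from one date in both arms: the treatment-phase completion or discontinuation date or, in Arm A, the last avelumab dose if that is later. Keep deaths within 30 days of last avelumab dose as an Arm A-only supportive row.

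Leave SAP 5.2.7 as the primary definition for treatment-emergent events. Add one supportive summary of treatment-emergent, serious and fatal adverse events using the common date, with the same new-therapy cut in both arms.

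The cost is one derived date and a few tables. Discontinuation of study drug is already reported for both arms (SAP 6.5.2.1). Adverse events are collected to 90 days after last dose in Arm A, and the new window ends g + 30 days after it, so coverage is complete up to g = 60 and incomplete beyond. Arm A percentages would rise slightly and be less comparable with tables based on last dose. Because Arm A visits are timed from last dose, the supportive window will not line up exactly with the 30-day visit; a footnote should say so.

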5.1. Allocation to Treatment

The investigator's knowledge of the treatment should not influence the decision to enroll a particular patient or affect the order in which patients are enrolled.

Qualified patients who have signed an Informed Consent Form and meet all eligibility criteria will be randomized in a 1:1 ratio to receive avelumab plus BSC (Arm A) or BSC alone (Arm B). Allocation of patients will be stratified according to best response to first-line chemotherapy (CR/PR vs. SD) and site of metastases (visceral vs. non-visceral) at the time of initiating first-line chemotherapy. The "non-visceral" stratum includes patients with locally-advanced disease as well as patients with only non-visceral disease. This stratified randomization will be centrally allocated across all centers using an Interactive Response Technology (IRT) system (an interactive web-based response system).

The site personnel (study coordinator or specified designee) will be required to enter or select information including but not limited to the user's identification (ID) and password, the protocol number, patient identifiers and demographic information, and stratification factors. The site personnel will then be provided with a treatment assignment. The IRT system will also provide a confirmation report containing the patient number; this confirmation report must be stored in the site's files.

Study treatment (Cycle 1 Day 1) must start within 3 days after patient randomization.

There is a 24-hour-a-day, 365-days-a-year IRT helpdesk available for any questions or issues. The study-specific IRT reference manual will provide the contact information and further details on the use of the IRT system.

Note: The IRT is the source of the patient number. The IRT system will provide the patient number at the end of the first IRT patient transaction.

Arm B patients who crossover to receive avelumab plus BSC will be assigned avelumab in the IRT system according to instructions provided by the Sponsor.

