8. Current or prior use of immunosuppressive medication within 7 days prior to avelumab treatment (Cycle CR1 Day 1), EXCEPT the following:
 - a. Intranasal, inhaled, topical steroids, or local steroid injections (eg, intra-articular injection);

- b. Systemic corticosteroids at physiologic doses ≤ 10 mg/day of prednisone or equivalent;
 - c. Steroids as premedication for hypersensitivity reactions (eg, CT scan premedication).
9. Diagnosis of prior immunodeficiency or organ transplant requiring immunosuppressive therapy.
10. Vaccination within 4 weeks of the first dose of avelumab treatment and while on trial is prohibited except for administration of inactivate vaccines (for example, inactivated influenza vaccines).
11. Breastfeeding female patients and female patients of childbearing potential who are unwilling or unable to use a highly effective method of contraception as outlined in the protocol [Section 4.3.1](#) for the duration of the study and for at least 30 days after the last dose of investigational product.
12. Other severe acute or chronic medical conditions including but not limited to HIV, HBV, or HCV infection, colitis, inflammatory bowel disease, pneumonitis, and pulmonary fibrosis; psychiatric condition including recent (within the past year) or active suicidal ideation or behavior; or laboratory abnormality that may increase the risk associated with study participation or study treatment administration or may interfere with the interpretation of study results and, in the judgment of the investigator, would make the patient inappropriate for entry into this study.

GENERAL TREATMENT/STUDY PLAN

Patients who crossover from BSC alone to avelumab plus BSC will receive avelumab at 10 mg/kg on Day 1 and Day 15 of each 4-week treatment cycle after all procedures/assessments have been completed as described in the [SOA](#) table.

With the exception of the detailed SOA provided below, all study treatments, concomitant medication restrictions, AE reporting, etc, described for patients randomized to Arm A in [Section 5](#) through [Section 7.1](#) and [Section 8](#) of the study protocol will be followed for patients who crossover from Arm B to avelumab plus BSC.

SCHEDULE OF ACTIVITIES FOR PATIENTS WHO CROSSOVER FROM ARM B TO AVELUMAB PLUS BSC

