2. INTRODUCTION

This SAP provides the detailed methodology for summary and statistical analyses of the data collected in study B9991001. This document may modify the plans outlined in the protocol; however, any major modifications of the primary endpoint definition or its analysis will also be reflected in a protocol amendment.

A separate SAP will cover the interim analyses for periodic safety review by the External Data Monitoring Committee (E-DMC).

Statistical analyses will be performed using cleaned eCRF data as well as non-CRF data (ie, pharmacokinetic [PK] concentration, anti-drug antibodies (ADA; neutralizing antibody [nAb]), supplemental biomarker data, and tumor assessment results by the Blinded Independent Central Review (BICR)).

The primary analysis will include all data up to a cut-off date which is determined by the number of events (deaths) required for the analysis of Overall Survival (OS) and a minimum follow-up of 12 months after the last patient is randomized. The cut-off date is determined once a data extract (before database lock) is available which indicates that the required number of events for OS in both co-primary populations and the minimum follow-up of 12 months is expected to occur by the cut-off date.

Due to data cleaning activities, the final number of events might deviate from the planned number. The data cut-off date will not be adjusted retrospectively in this case.

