4.2. Safety Analysis Set

The safety analysis set will include all patients who receive at least one dose of study drug on Arm A or completed C1D1 on Arm B. If a patient randomized to Arm B incorrectly receives avelumab, then the patient will be classified in Arm A for the purpose of safety analyses.

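### The SAP supplied has no crossover rule for safety, so in any safety table cut after crossover opened, adverse events on crossover avelumab would be counted under BSC alone

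*SAP*

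**What the plan says.** SAP 5.2.7, repeated in 3.5.1, defines the period over which Arm B safety data are summarized: "Arm B: time from Cycle 1 Day 1 through minimum (30 days + end date of BSC, start day of new anti-cancer drug therapy", less one day. Both end terms come from specific eCRF pages:

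- End date of BSC "is the date of completion or discontinuation as collected in the" treatment-phase disposition page.
- New anti-cancer drug therapy, under SAP 5.2.5, is "the earliest start date of anti-cancer drug therapy recorded in the" follow-up cancer therapy pages.

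The safety analysis set has one reassignment rule (SAP 4.2): "If a patient randomized to Arm B incorrectly receives avelumab, then the patient will be classified in Arm A for the purpose of safety analyses".

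Immune-related events (irAEs) have their own window. Appendix 1, Table 16, Step 2 accepts onset up to 90 days after the last dose of study treatment, whether or not the event is treatment-emergent. For Arm B, SAP 3.4.1 equates last dose with the end date of BSC. The same anchor governs the table of deaths within 30 days of last dose in SAP 6.6.2.

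On the protocol side, Section 5.1 states "Arm B patients who crossover to receive avelumab plus BSC will be assigned avelumab in the IRT system", and Supplement 1 adds "Patients who crossover from BSC alone to avelumab plus BSC will receive avelumab at 10 mg/kg on Day 1 and Day 15" of each 4-week cycle. Supplement 1 also requires that the End of Treatment visit has not yet taken place and keeps adverse events on the CRF to 90 days after the last avelumab dose. It extends the Arm A rules of Sections 5 to 7.1 and 8 to these patients, but nothing from Section 9, which holds the analysis rules.

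**The concern.** The safety tables compare arms, and SAP 6.6.4 adds risk differences with confidence intervals for irAEs and for common events. An avelumab event booked to BSC alone raises the comparator rate and makes the excess harm of avelumab look smaller. Nothing in the SAP's Arm B window or in its reassignment rule stops this for a patient who crosses over as the protocol permits. The overlap also falls on the first infusions, when most infusion-related reactions (IRRs) begin according to the protocol's own background data.

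**Working it through.** The plan states no figure for this point, so the check is to apply its rules to a crossover patient and then size the result.

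**Step 1. Does either end term fire at crossover?**

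- *New anti-cancer drug therapy.* This is read only from the follow-up cancer therapy pages. Crossover avelumab is study drug allocated through IRT. Supplement 1's end-of-treatment and follow-up schedule has a separate row for new systemic anticancer treatment, so the protocol treats the two as different things.
- *End date of BSC.* This is a disposition date. Supplement 1 continues BSC alongside avelumab and schedules follow-up from the last avelumab dose. The documents do not say when the treatment-phase disposition page is completed for these patients, so both possibilities are carried forward.

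The reassignment rule in SAP 4.2 does not apply, because a permitted crossover is not an incorrect receipt. Protocol 9.2.3 likewise keeps patients in their randomized arm unless incorrect treatment is received throughout the dosing period.

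**Step 2. How much avelumab treatment falls inside the Arm B window?** Let day 0 be the first crossover dose, with doses every 14 days.

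- *Reading A, page closed when crossover treatment ends.* The window closes 30 days after the last dose. With 6 doses the last is on day 5 × 14 = 70 and the window ends on day 100. With 13 doses the last is on day 12 × 14 = 168 and it ends on day 198. Every dose is inside.
- *Reading B, page closed on the day of crossover.* The window ends on day 0 + 30 = 30 and takes in doses on days 0, 14 and 28. Visits may move by 3 days, so the third dose sits near the edge. Later events are listed but not summarized.

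Under neither reading does the window stop at crossover.

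**Step 3. Immune-related events.** Under Reading B the Appendix 1 window runs to day 90 and takes in doses on days 0, 14, 28, 42, 56, 70 and 84. Under Reading A it covers all crossover treatment. This follows from Table 16, not from SAP 5.2.7, so changing 5.2.7 alone would not correct it.

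**Step 4. Background rates.** These come from the pooled expansion cohort of 717 patients in Protocol 1.2.2.1.

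- IRR onset by infusion: 91, 35, 9 and 3 patients, total 138. The stated percentages reproduce: 91/717 = 12.7% and 35/717 = 4.9%.
- Onset at infusion 1 or 2: 126/138 = 91.3% of patients with an IRR. Through infusion 3: 135/138 = 97.8%.
- Rate per treated patient at infusion 1 or 2: 126/717 = 17.6%.
- Any treatment-related TEAE: 498/717 = 69.5%, as stated.

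**Step 5. Illustrative size.** Arm B has 668/2 = 334 planned patients. The crossover share is not in the documents; 3–10% is assumed, giving 0.03 × 334 = 10.0 to 0.10 × 334 = 33.4 patients.

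- IRRs under BSC alone: 10.0 × 0.176 = 1.8 to 33.4 × 0.176 = 5.9, so about 2–6 patients (0.5–1.8% of 334). Only the first two infusions are counted, so this applies under both readings.
- Patients with a related TEAE, Reading A only: 10.0 × 0.695 = 7.0 to 33.4 × 0.695 = 23.2, so about 7–23 patients (2–7% of 334).

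**The case against.** The strongest objections concern reach and size, not the rule itself.

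- *The sponsor failed to update the SAP.* A reader might infer this, but the documents do not show it. The SAP supplied is dated 2 April 2019, and Amendment 5 followed on 13 February 2020. A later version or addendum may exist. What can be said is that the version supplied has no crossover rule.
- *Safety tables are planned at the 425/219-death cut.* The protocol (1.2.3.3) calls that analysis a final OS update and does not say that between-arm safety tables will be re-run. The point is therefore conditional on a safety output being produced after crossover opened.
- *The extent depends on eCRF design.* Supplement 1 has its own consent, cycle numbering and baseline symptom record, which would be compatible with closing the disposition page at crossover. That would limit ordinary TEAEs to about 30 days. It would not remove the overlap, and irAEs would still be counted to 90 days.
- *The numbers are soft.* The crossover share is an assumption, and the background rates come from pooled solid-tumor cohorts rather than from long-term progression-free Arm B patients. This stands.
- *An IRR under BSC alone would be noticed.* Appendix 2 ties IRRs to an intravenous infusion, so an entry there would stand out and could be traced. This also stands, but ordinary TEAEs and irAEs carry no such marker.

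**Conclusion.** The point holds for the SAP supplied and for any safety output with a cut-off after crossover opened. On either reading of the end date of BSC, the written rules put avelumab events in the BSC-alone column, and the bias favors avelumab. Under the assumed 3–10% crossover share and the protocol's background rates, about 2–6 IRRs would be misplaced. The figure of about 7–23 patients with related TEAEs also requires the disposition page to stay open throughout crossover treatment, so it is an upper case and not an expectation.

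It would be wrong to infer that the interim safety output is affected, because crossover was opened only after that analysis. Nor does the point touch overall survival, which is analyzed by randomized arm without reference to the on-treatment period. It is a gap between a SAP written before crossover and a protocol amended to allow it. It should be closed before any post-crossover safety table is produced.

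**What to change.** 1. In SAP 3.5.1 and 5.2.7, end the Arm B period at the earliest of three dates: end date of BSC plus 30 days; the day before new anti-cancer drug therapy; the day before the first dose of crossover avelumab.
2. Apply the same crossover cut for Arm B in Appendix 1, Table 16, Step 2, and in the 30-day death table of SAP 6.6.2.
3. State in SAP 4.2 that crossover patients remain in Arm B for their pre-crossover period.
4. Summarize events from the first crossover dose onward in a separate crossover column, outside the between-arm risk differences.

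The cost is SAP wording, one extra table column and slightly less Arm B follow-up time. The dose dates needed are already collected.
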